2.2 Current state of our own research

PedAMINES: Following a user-centered and evidence-based approach⁴⁵, our group composed of PED physicians and nurses, as well as software developers and ergonomists has developed a tablet app called Pediatric Accurate Medication in Emergency Situations (PedAMINES). This app is a supportive tool designed to drive caregivers step-by-step and in real-time from preparation to delivery of a wide range of drugs, especially those required during resuscitation. The app development was mainly guided by requirements built on our clinical experience, CPR observations and focus groups⁴⁶. In an in-hospital pilot randomized trial, we have shown that medication errors were reduced from 70% to 0% ($P<.001$) by using PedAMINES when compared with conventional methods. Time to drug preparation (TDP) and delivery (TDD) were decreased by 180 and 177.3 seconds respectively ($P=.002$)⁴⁷. Results were by far better than those, already consequent, obtained with the on-site presence of clinical pharmacist during pediatric CPRs associated with a 25% decrease in medication errors¹⁶.

Granted by the *Swiss National Science Foundation* (SNSF #**32003B_169348/1**), we next conducted in 2017 a multicentric opened randomized controlled crossover trial in 6 PEDs in Switzerland with the same simulation-based scenario with more than 120 nurses (forthcoming publication). Medication errors were reduced from 75.9% to 10.2% by using PedAMINES when compared with conventional methods ($P<.0001$), while using PedAMINES TDP and TDD were reduced by 141.8 (43.9%) and 161.9 (39.0%) seconds respectively (both $P<.0001$, Figure 1). Participants rated the overall perceived satisfaction using PedAMINES to be 9.4 (95% CI 9.3-9.6) on a 10-point Likert scale.

[figure not shown]

Fig 1. Boxplots of elapsed time to drug preparation (TDP) and to drug delivery (TDD) in intervention group (PedAMINES) and control group (conventional method) in both periods of the SNSF crossover study. Time is expressed in seconds. Solid horizontal lines denote median and interquartile ranges; the whiskers go down to the smallest value and up to the largest; + denotes mean. Red open circles denote each individual value. Time is expressed in seconds. P-values are the result of Mann-Whitney test. **** $P<.0001$.

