Resuscitation scenario: the untimed portion of the simulation starts by turning on the video cameras and the fitness watch. The paramedic and both investigators (the confederate paramedic and the physician) wait outside the room where they are supposedly dispatched. The team will be invited to enter the room by the father (simulated by the technician operating the manikin). A clinical statement to recognize the life-threatening condition of the patient, including his weight and age, is then given by the father as follows: "Here is Junior, a 12-kg, 1 and a half year old boy who suddenly collapsed 15 minutes ago. Oral tricyclic antidepressant as well as antidiabetic pills from his grandmother were found in his mouth and on the ground of his room. He is unconscious, pale and does not breathe". At this moment, the physician asks the participant to take a central pulse. Because of the invariable absence of a pulse, the latter is asked to assist the physician to perform a 2-min full course massage and ventilation (15:2 ratio) maneuver to increase his own stress level (massage carried out by the participant). During this time, the physician asks the confederate paramedic to place a 4-derivation electrocardiogram on the manikin, an upper arm blood pressure monitor, a digital pulse oximeter and defibrillator's patches. Then the physician asks to change roles; the confederate paramedic has to carry out the massage while the participant has to get a peripheral vascular access on the manikin's right hand. At this time, an asystole rhythm is recognized and verbalized by the physician. On the basis of the American Heart Association pediatric cardiac arrest algorithm for asystole⁴, a bolus of epinephrine is ordered by the physician and the timed scenario begins. The participant must prepare and administer the drug with the help of PedAMINES (intervention group) or following the conventional method. ROSC ensues with generalized tonic-clonic seizures. The physician says: "The patient has now a return of spontaneous circulation with a pulse but with seizures. This patient needs an IV bolus of midazolam right now". The seizures stop 15 seconds after administration of the drug. At this time the physician asks the participant to perform a finger stick to obtain a blood sample. The glucometer reports a blood sugar of 0.8 mmol/L. The physician says: "the patient has a severe

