C) *Questionnaires*: at the end of the scenario, a 6-item questionnaire using a 10-point Likert scale (scored from one to ten to avoid neutral answers) will be provided to the participants. The questionnaire measures (1) the overall stress perceived, (2) the stress perceived during each drug preparation sequence with PedAMINES and with the conventional method(s), and (3) the satisfaction about the preparation method used during the resuscitation scenario. Acceptability and usability testing of the app will be assessed using a 52-item questionnaire based on the unified theory of acceptance and use of technology (UTAUT) model⁵⁴. UTAUT provides a useful tool to assess the likelihood of success for new technology introductions and helps to understand the drivers of its acceptance.

D) *Heart rate (HR) as a stress marker*: a baseline HR before the beginning of the scenario as well as continuous HR monitoring of each participant reflecting his or her stress level will be recorded during the scenario. Mean delta HR values (difference between HR peak values and baseline HR) will be obtained during some small segments of scenario and correlated to the scenario phases and the preparation methods used.

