2.3.14.2. Statistical methods for additional analysis

For the primary and secondary outcomes, logistic regression analyses will be conducted to test a difference in rates of errors between urban EMS (defined as a primary EMS agency in a area populated with 50,000 or more people in the immediate proximity of a tertiary care PED)⁵⁶ and rural EMS (i.e. EMS agency not included within an urban area) with PedAMINES and with the conventional preparation method. In a GEE logistic regression model, an interaction between interventions and urban/rural EMS will be tested to investigate a potential modification of the efficacy of PedAMINES in rural area compared with urban area. Results will also be correlated to the EMS exposition (i.e. total number of emergency calls per year per EMS divided by the number of paramedics working in that EMS). Analyses of primary and secondary outcomes will be conducted in paramedics with more or less than 10 years of experience.

Means and standard deviations will be determined for stress and satisfaction scores (Likert scale) of individuals for each questionnaire item as well as for the UTAUT questionnaire and reported with descriptive statistics. Pearson correlations will be computed between the HR measures obtained with the watch and the scenario phases for each of the drugs and preparation methods used.

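### The heart-rate stress marker is a peak over undefined segments analysed by Pearson correlation; if segments follow the self-paced drug phases, arms can differ at equal stress, and no arm difference is estimated either way

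*Combined protocol and SAP*

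**What the plan says.** The Summary lists perceived and measured stress among the secondary outcomes. Section 2.3.6 D records "a baseline HR before the beginning of the scenario as well as continuous HR monitoring of each participant". It then sets the marker: "Mean delta HR values (difference between HR peak values and baseline HR) will be obtained during some small segments of scenario", to be "correlated to the scenario phases and the preparation methods used". The number of segments, their length and their starting point are not stated.

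The only analysis is in section 2.3.14.2: "Pearson correlations will be computed between the HR measures obtained with the watch and the scenario phases for each of the drugs" and preparation methods. No adjustment for phase duration or prior exertion is mentioned.

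Three other places bear on this:

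- Section 2.3.5.1: after the baseline, every participant performs 2 minutes of chest compressions. Roles then change: "the confederate paramedic has to carry out the massage while the participant has to get a peripheral vascular access". The rhythm is recognised next, and only then is epinephrine ordered.
- Section 2.3.5.1: the study team adapts to the participant's speed, so phase lengths are self-paced.
- Section 2.3.2: the trial hypothesises shorter preparation and delivery times (TDP, TDD) with the app. Section 2.2 reports for the earlier crossover trial that "TDP and TDD were reduced by 141.8 (43.9%) and 161.9 (39.0%) seconds respectively".

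**The concern.** The expected maximum of a fluctuating series rises with the length of the window. If a segment is a drug phase, as the wording of section 2.3.14.2 suggests, the arm with longer phases has the higher expected peak even when stress is the same.

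The baseline is taken before the compressions, so peak minus baseline also contains whatever exertion has not yet worn off. An arm that moves faster through the script reaches the second and later orders with more of it left.

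The analysis adds a separate difficulty. Phase and preparation method are categories. A Pearson correlation with them does not give a difference between arms in bpm with an interval, which is what a reader of a randomised comparison needs.

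At stake is whether a reported difference in measured stress can be read as stress at all. Leaving the segments undefined also allows them to be chosen after the recordings have been seen.

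**Working it through.** The plan gives no design figure for heart rate, so there is none to reproduce. Every bpm figure below rests on assumptions that are not in the documents. Differences are control minus app.

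**1. How much shorter are the app phases?**
- Section 2.2: control TDD = 161.9 / 0.390 = 415 s; app = 415 − 162 = 253 s.
- The Summary gives other figures for the same trial: 170.5 / 0.39 = 437 s; app = 437 − 170.5 = 267 s.
- Both imply a 39% reduction. The absolute times do not fit this trial: 4 × 415 s = 1,660 s = 27.7 min, against a scenario of about 20 min. After 2 min of compressions at most (1,200 − 120) / 4 = 270 s per drug remain.
- I therefore keep the ratio and assume control phases of 150 or 250 s (app 92 or 152 s).

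**2. Length effect alone (equal stress, no carry-over).** Heart rate is simulated as a stationary autocorrelated series, 8,000 participants per arm. Assumed within-person SD is 4 to 8 bpm and correlation time 10 to 30 s. Difference in mean whole-phase peak:
- app phases 39% shorter: +0.9 to +2.2 bpm;
- app phases 20% shorter: +0.3 to +1.1 bpm;
- mean over the phase, or peak in a fixed 30 s window: within about 0.2 bpm of zero.

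**3. Carry-over from compressions.** Residual at time t after compressions = A·exp(−t/τ). Assumed: A = 20 to 30 bpm, τ = 60 to 120 s, 60 s for vascular access, 30 s between drugs, phases 150 v 92 s.
- Epinephrine order: t = 60 s in both arms, so the difference is 0.
- Second order: app t = 60 + 92 + 30 = 182 s; control t = 60 + 150 + 30 = 240 s.
- A = 30, τ = 120: app 30·exp(−182/120) = 6.6; control 30·exp(−240/120) = 4.1; difference −2.5 bpm.
- A = 20, τ = 60: app 20·exp(−182/60) = 0.96; control 20·exp(−240/60) = 0.37; difference −0.6 bpm.
- Averaging over the first 60 s multiplies these by (1 − exp(−60/τ)) / (60/τ), which is 0.787 or 0.632, giving −2.0 and −0.4 bpm.
- By the fourth order, with A = 30 and τ = 120: app t = 60 + 3 × 122 = 426 s, control t = 60 + 3 × 180 = 600 s; 0.86 − 0.20 gives −0.7 bpm.

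**4. Both together.** Across the simulated settings with 39% shorter app phases and A from 0 to 30 bpm, the whole-phase peak differs by −1.4 to +2.2 bpm. The effects partly cancel and the sign is not fixed.

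**5. What a bias of this size would do to an arm comparison.** With 60 per arm and an assumed SD of the marker of 10 to 15 bpm, SE = SD·√(2/60) = 1.83 to 2.74 bpm. For a two-sided 5% test:
- 1 bpm bias: rejection probability 7 to 9%;
- 2 bpm bias: 11 to 20%.

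**6. Change score against covariate adjustment.** With equal variances and baseline correlation r, the variance ratio is (1 − r²) / [2(1 − r)] = (1 + r)/2. For r = 0.3 this is 0.65; for r = 0.7 it is 0.85.

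**The case against.** The strongest reply is that small segments may mean short windows of equal length. The length effect would then vanish. This stands: a reader might infer that segment length does differ by arm, and the documents do not say so. What they show is that the definition is missing.

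A reader might also infer that time since compressions differs by arm throughout. It does not. The epinephrine order comes at the same scripted point, before the allocated method has been used, so carry-over there is balanced in expectation. The imbalance arises later in that phase and at drugs 2 to 4.

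Nor should the earlier trial's 253 s and 415 s be used as recovery times here. They do not fit the 20-minute scenario, and they leave out vascular access. With A = 50 bpm and τ = 120 s, the app-arm residual is 50·exp(−253/120) = 6.1 bpm; adding an assumed 60 to 90 s for access lowers it to 3.7 to 2.9 bpm.

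The change score is not biased under randomisation; replacing it only gains precision. It is also fair to say that heart rate is one of many secondary measures, that its analysis sits under additional analyses, and that perceived stress is collected separately by questionnaire. These points limit the importance. They do not supply the missing definition or an estimate of the arm difference.

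**Conclusion.** The point holds in a limited form. As written, the marker can show an arm difference of roughly 1 to 2 bpm at equal stress, if segments follow the drug phases and app phases are 39% shorter. Exertion carry-over pulls the other way at later drugs, mainly drug 2. The documents do not support a claim that the net bias favours either arm. Its sign and size depend on assumed heart-rate variability, recovery and phase lengths.

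Two parts need none of these assumptions: segment length and anchor are unspecified, and the planned correlations do not estimate an arm difference.

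This is a minor, inexpensive improvement to a secondary outcome.

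**What to change.** Before the heart-rate data are examined, amend sections 2.3.6 D and 2.3.14.2 as follows:

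- Replace the peak by mean heart rate over a window of the same fixed length in both arms, starting at the end of each drug order (for example the first 60 s).
- Replace the change score and the Pearson correlations by a linear mixed model with arm, drug, arm-by-drug interaction, a random intercept for paramedic, and baseline heart rate as covariate. Report the arm difference with 95% CI, overall and by drug. Section 2.3.14.1 already plans a random-intercept linear model adjusted for drug for TDP and TDD.
- Treat the epinephrine window as the comparison free of differential carry-over. Exertion is still present there, but equally in both arms.
- For drugs 2 to 4, report time since compressions by arm and interpret those windows with that caveat.
- Keep the peak as a descriptive summary.

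The cost is wording only. The watch records throughout the scenario, and the end of each order is already the start point for TDP. There are two drawbacks: a short spike late in a preparation is missed, and carry-over at drugs 2 to 4 is disclosed but not removed (about 0.4 to 2.0 bpm at drug 2 in the example above, higher in the app arm).

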2.3.7. Patients Timeline

On-site staff in every collaborating EMS will organize participation of paramedics to the study. No information about the ongoing study will be given to the paramedics at this stage. The best study period will be matched with study coordinators. The paramedics will be spread throughout 1 week in order to link up the several scenarios. On scheduled weeks, the study coordinators will visit the collaborating EMS, provide trial information to participants before they begin the scenario, and assessment of eligibility will be verified. Participants will then sign the informed consent. They will be asked to complete an anonymised demographic questionnaire and confirm their willingness to participate. If it's the case, they will pursue with a 5-minute learning session to the use of PedAMINES given by the investigators. Then, each participant will be randomly allocated to study arms. Immediately after the randomization, the paramedic will start the scenario. 1) the overall stress perceived during the scenario and during each drug preparation, and 2) the satisfaction about the preparation method used. The total study period to enroll all paramedics in the various EMS will take 12 months.

Table 1. PedAMINES timeline protocol for forms and procedures

	Study Period				
	Pre-enrollment	Enrollment / consent	Pre-study baseline / allocation	20-minute scenario	Closeout
Time point	$-t_2$	$-t_1$	0	t_1	t_x
ENROLMENT:					
Invitation to participate	X				
Eligibility screen		X			
Informed consent form		X			
Demographic questionnaire			X		
PedAMINES learning session			X		
Randomization			X		
INTERVENTION :					
Group A (with PedAMINES)				X	
Group B (with conventional method)				X	
Termination questionnaire					X
ASSESSMENTS :					
Medication errors				X	
Time at prescription				X	
Time to drug preparation (TDP) and delivery (TDD)				X	

2.3.8. Sample size

The primary objective of this study is to detect a difference in proportions of medication errors between groups (with PedAMINES vs without PedAMINES). The expected proportion of errors made without PedAMINES is 60%¹¹. We consider that a difference of 30% in the proportion of medication errors is sufficient to modify the practice. Therefore, the sample size was calculated to reach a statistical power of 90% in detecting an absolute difference of at least 30% in proportions of medication errors between intervention groups. With a two-sided risk alpha of 0.05, the needed sample size is 56 paramedics per arm of the study. To prevent a potential loss of power due to misspecification of assumptions, 60 paramedics will be recruited per randomized group (total sample size: 120 paramedics).

2.3.9. Recruitment

2.3.9.1. Recruitment strategies

We already have the study participation approval of the different EMS. Each collaborating EMS will organize a dedicated time slot for the study to be run and paramedics to be available at the defined period. In case of unavailability of a paramedic at the selected date, the collaborating EMS will handle to replace him. The investigators and collaborating EMS will be in close contact by phone/email to guarantee availability of the paramedics.

2.3.9.2. Feasibility of recruitment

The number of available paramedics will be guaranteed by the collaborating EMS knowing their absolute workforces and the paramedics working shifts. Given the calculated sample size, the number of paramedics is affordable.

2.3.10. Assignment of intervention

2.3.10.1. Allocation sequence

A single randomization of the participants (paramedics) will be done using an online computing web randomisation service⁵⁵ to generate the randomisation list. With this method, paramedics will be randomly assigned to either group A (using PedAMINES) or to group B (conventional preparation methods) with a single, constant 1:1 allocation ratio. One randomization list per EMS center will be produced (randomization stratified on center) and block of random size will be used to generate the randomization lists.

2.3.10.2. Concealment mechanism

Allocation concealment will be ensured with <http://www.sealedenvelope.com> and will not be released until the paramedics start the scenario.

2.3.10.3. Implementation

The allocation sequence will be generated by <http://www.sealedenvelope.com> and the randomization lists will remain with it for the whole duration of the study, ensuring that the investigators couldn't influence the lists. The paramedics will be enrolled and assigned to the allocation groups by the investigators of the study on the day of the simulation.

2.3.11. Blinding

2.3.11.1. Blinding

Blinding to the purpose of the study during recruitment will be maintained to minimize preparation bias. The paramedics will be unblinded after randomization. The study team members will be revealed just before the scenario starts, and video reviewing will be done without blinding by both video reviewers but independently and blindly from one another.

2.3.11.2. Emergency unblinding

At the time of the simulation, paramedics and investigators are not blinded. Since our study is held on a high-fidelity manikin, the patients or paramedics incur no risk.

2.3.12. Data collection

2.3.12.1. Data collection methods

Research using simulation has a valid and reliable investigative methodology to study factors affecting human and systems performance in health care has been reviewed⁵⁰. In this project, we will use simulation as an investigative methodology to assess the primary and secondary outcomes described above.

All the actions (ie, primary and secondary outcomes) performed by the paramedics during the scenario will be automatically recorded and stored by the responsive simulator detectors (Leardal SimBaby) and by 3 GoPro Hero 5 Black edition (GoPro Inc) video cameras. The setup of the 3 cameras will be standardized to record at a resolution of 1080p, at 90 frames per second, wide field of view, and with a 16:9 aspect ratio. Cameras position will be standardized. The first camera will be placed in a head strap on the paramedic's head with an inclination of 45° downwards to film the front scene. The second camera will be placed on a tripod in front of the nurse and the manikin, slightly above the head height, with an inclination of 90° downwards to film the place where the drugs will be prepared. The third camera will be placed on a tripod 1 meter away from the paramedic on his or her left (if right-handed) or right (if left-handed) and at the level of the navel to film the scene on the side. All actions performed with PedAMINES will be automatically saved locally in log files for further analysis. The validity and reliability of

the app has been assessed in a prior study⁴⁷. Participants' HR will be recorded during the entire resuscitation scenario with the HR monitor on a Polar A360 watch (Polar Electro Oy). The data will be stored on the wristwatch itself with further analysis being accomplished offline. On-site, the investigators will double-check that the questionnaires are fully and accurately filled.

2.3.12.2. Retention

Our study offers the advantage of being very short in duration, around 60 minutes per paramedic. Therefore, neither follow-up nor retention plans will be necessary. The intervention protocol is highly standardized, and paramedic deviation from protocol in terms of drug preparation is a parameter that is of interest in our study (ie, in terms of medication errors or delays in drug preparation).

2.3.13. Data management

Data collected during the interventions will be entered in EpiData database (EpiData, software v3.1, EpiData Association, Denmark) by the investigators of the study, in anonymised form. To avoid assessment bias, 2 evaluators will then independently review the video recordings. In case of disagreement, a third independent evaluator will help reach a consensus. In order to assess interrater reliability on video reviewing, a kappa score will be calculated.

